#### Tolerability

- 4) Occurrence of premature discontinuation of study treatment, including reasons for discontinuations.

#### Efficacy

- 5) Participant-specific change in log10-transformed plasma IL-6 (using geometric means of two ELISA measurements at pre-entry and entry, and weeks 4 and 5).

#### **2.4.2 Secondary Outcome Measures**

- 1) Proportion of participants on Ruxolitinib who experienced any of the following safety milestones during study follow-up from entry through week 12.
- o For participants with entry CD4+ T cell count  $< 700$  cells/mm^3, confirmed CD4+ decline  $> 33\%$  of baseline and to  $< 350$  cells/mm^3.
  - o For participants with entry CD4+ T cell count  $\geq 700$  cells/mm^3, a confirmed CD4+ T cell decline  $> 50\%$  of baseline.
  - o Confirmed HIV-1 RNA level above the lower limit of quantification in the absence of an interruption in ART.
  - o New or recurrent CDC category C AIDS-indicator condition.
  - o HIV-1 associated infection including Herpes zoster.
  - o Lymphoproliferative malignancies.
  - o Discontinuation of ruxolitinib due to thrombocytopenia.
  - o Grade 4 or recurrence of Grade 3 anemia/neutropenia.
  - o Any Grade 4 or recurrence of Grade 3 toxicity related to study drug.
  - o New diagnosis of pneumonia, sepsis, or bacteremia.

- 2) Proportion of participants who experienced any of the following safety milestones during study follow-up from entry through week 12 by study arm:
  - For participants with entry CD4+ T cell count  $< 700 \text{ cells/mm}^3$ , confirmed CD4+ decline  $> 33\%$  of baseline and to  $< 350 \text{ cells/mm}^3$ .
  - For participants with entry CD4+ T cell count  $\geq 700 \text{ cells/mm}^3$ , a confirmed CD4+ T cell decline  $> 50\%$  of baseline.
  - Confirmed HIV-1 RNA level above the lower limit of quantification in the absence of an interruption in ART.
  - New or recurrent CDC category C AIDS-indicator condition.
  - HIV-1 associated infection including Herpes zoster.
  - Lymphoproliferative malignancies.
  - Occurrence of Grade 2 or higher thrombocytopenia.
  - Grade 4 or recurrence of Grade 3 anemia/neutropenia.
  - Any Grade 4 or recurrence of Grade 3 toxicity.
  - New diagnosis of pneumonia, sepsis, or bacteremia.
- 3) Proportion of *each* of the following components that occurred during study follow-up from entry to week 12 by study arm:
  - For participants with entry CD4+ T cell count  $< 700 \text{ cells/mm}^3$ , confirmed CD4+ decline  $> 33\%$  of baseline and to  $< 350 \text{ cells/mm}^3$ .
  - For participants with entry CD4+ T cell count  $\geq 700 \text{ cells/mm}^3$ , a confirmed CD4+ T cell decline  $> 50\%$  of baseline.
  - Confirmed HIV-1 RNA level above the lower limit of quantification in the absence of an interruption in ART.
  - New or recurrent CDC category C AIDS-indicator condition.
  - HIV-1 associated infection including Herpes zoster.
  - Lymphoproliferative malignancies.
  - Occurrence of Grade 2 or higher thrombocytopenia.
  - Grade 4 or recurrence of Grade 3 anemia/neutropenia.
  - Any Grade 4 or recurrence of Grade 3 toxicity.
  - New diagnosis of pneumonia, sepsis, or bacteremia.
- 4) Occurrence of protocol-defined reportable adverse events (all diagnoses, Grade 3 or higher sign/symptoms or laboratory values, any signs/symptoms or laboratory values that led to a change in treatment or met ICH, EAE, or SAE guidelines) at any post-entry time point.
- 5) Safety Laboratory values (estimated creatinine clearance, creatinine, AST (SGOT), ALT (SGPT), ANC, hemoglobin, platelet count) across all study weeks (at entry, week 1, and week 2, and arithmetic means at weeks 4 and 5, and at weeks 10 and 12).
- 6) Change in safety laboratory values (estimated creatinine clearance, creatinine, AST (SGOT), ALT (SGPT), ANC, hemoglobin, and platelet count) across all study weeks (at weeks 1 and 2, and arithmetic means at weeks 4 and 5 and at weeks 10 and 12).
- 7) Change in log10-transformed plasma IL-6 across all study weeks (geometric means of pre-entry and entry, and week 10 and 12).
- 8) Changes in soluble markers of immune activation and inflammation in the peripheral blood (sCD14, TNF- $\alpha$ , IL-1 $\alpha$ , IL-1 $\beta$ , IL-7, IL-10, IP-10, IL-18, mCSF, and neopterin) across study weeks from baseline (geometric mean of pre-entry and entry) to week 4/5 (geometric mean of week 4 and week 5) and week 12.

- 9) Changes in cellular markers of immune activation and inflammation in the peripheral blood (HLA-DR, CD25, CD38, CD69, CD127, Ki67, BCL2, a4b7, CX3CR1, PAR-1 measured on CD4 and CD8 cells; monocyte subsets (classical, inflammatory, and patrolling) defined by CD14 and CD16 expression; proportion of monocyte subsets (classical, inflammatory, and patrolling) expressing CCR2, CX3CR1, and CD163) from entry to weeks 5 and 12.
- 10) Level of plasma HIV-1 RNA at baseline and weeks 2, 5, and 12.
- 11) Change in CD4+ T cell counts from baseline (mean of pre-entry and entry) to weeks 2, 5, and 12.
- 12) Changes in HIV-1 reservoir (HIV-1 RNA by SCA, cellular HIV-1 total RNA and DNA) from entry to weeks 5 and 12.
- 13) Level of CMV shedding at pre-entry, entry, and weeks 1, 2, 4, 5, 10, and 12.

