5.0 STUDY TREATMENT

5.1 Regimens, Administration, and Duration

Study treatment is defined as ruxolitinib. **Participants** will be randomized at a 2:1 ratio to either 5 weeks of treatment with ruxolitinib or no study treatment as follows:

ARM A: Ruxolitinib 10 mg PO BID with or without food. **Participants must remain on ART regimen (not provided by the study) for the duration of the study.**

ARM B: No study treatment. **Participants should be encouraged to remain on ART regimen for the duration of the study.**

Participants in Arm A should be instructed not to drink grapefruit juice **or eat grapefruit** while taking ruxolitinib. **Participants** will remain on study treatment for five weeks and **be** followed for seven weeks after treatment discontinuation. **Participants** will be on study for **a total of** 12 weeks.

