6.3.5 Clinical Assessments

Height

Height (in cm) will be measured at the entry visit.

Weight

Weight (in kg) will be measured at screening, entry and at all subsequent study visits.

Signs and Symptoms

At entry, all grades that occurred 30 days before entry must be recorded; postentry, only signs and symptoms Grade \geq 2 must be recorded except record all non-traumatic bruising regardless of grade. All Grade 3 or higher sign/symptom, any sign/symptom regardless of grade that led to a change in treatment, or that met ICH, EAE, or SAE guidelines, are defined by the protocol as reportable events that will require more detailed event reporting and must be reported on the CRF within 2 business days.

Diagnoses

At entry and on-study visits, record all diagnoses identified by the ACTG criteria and any of the following targeted diagnoses occurring since the last study visit:

• New onset seizures; or physician diagnosed CNS abnormality.

Post entry diagnoses must be reported on the CRF within 2 business days.

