9.6 Analyses

9.6.1 Primary Analyses

A5336 FINAL Version 2.0 05/21/15

As this is a pilot study of biologic activity, our primary analysis of efficacy will be an as-treated analysis, limited to **participants** who meet all of the following conditions: (a) have data at baseline and week 5, (b) for the ruxolitinib arm, remain on study treatment through week 5 and miss no more than 6 doses cumulatively, (c) did not change ART, use prohibited medications, or have a virologic failure during this time period.

Changes from baseline to week 5 in plasma IL-6 (on log_{10} scale) will be summarized with the mean and a 90% confidence interval (CI) for the mean change in each treatment arm, and compared between arms with a t-test. The baseline value will be calculated as the geometric mean of pre-entry and entry, and the week 5 value as the geometric mean of weeks 4 and 5. If missing one of the pre-entry or entry values, then the available measure will be used as the baseline value, and similarly, if missing one of the week 4 or week 5 values, then the available measure will be used as the week 5 value.

Safety will be evaluated by estimating the proportion of participants in the ruxolitinib arm who experienceing the primary safety outcome measure 9.2.1.1. In addition, safety will be compared between the treatment arms via a one-sided Fisher's exact test at 5% alpha level, in terms of 9.2.1.1, but with this composite safety outcome modified to address the A5336 design where Arm B does not receive any study treatment. Specifically "discontinuation of ruxolitinib due to thrombocytopenia" will be modified to "occurrence of Grade 2 or higher thrombocytopenia" and "any Grade 4 or recurrence of Grade 3 toxicity related to study drug" will be modified to "any Grade 4 or recurrence of Grade 3 toxicity." Tolerability will be evaluated by summarizing treatment modifications and discontinuations.

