9.6.2 Secondary Analyses

Participant-specific changes from baseline to week 5 in other measurements of immune activation and inflammation, and CD4+ T-cell counts will be summarized similarly to the primary efficacy measure, via means and 90% CIs for the mean change for each of the study arms. The log₁₀ transformation is planned for various soluble and cellular markers. Comparisons between study arms will be done via the Wilcoxon rank sum test. HIV-1 RNA will be summarized by the number of **participants** with confirmed HIV-1 RNA > 40 copies/mL and > 200 copies/mL. Due to an anticipated high proportion of lower limit of detection censoring, levels of HHV shedding will be compared between arms at week 5 using a two-group Wilcoxon rank-sum test with 2-sided alpha=0.10 level. Values below the lower limit of detection will be analyzed as the lowest rank. In the event of limited lower limit of detection censoring, repeated measure modeling will be used to explore longitudinal changes in HHV shedding.

Safety events (signs and symptoms, laboratory values, diagnoses, and other SAEs) will also be evaluated by summarizing the nature and rate of AEs within

each study arm. Comparisons of overall and toxicity-specific grades between study arms will be shown descriptively.

Longitudinal changes from baseline to week 12 in all measures will be examined via descriptive summaries and plots.

Statistical significance will be tested using a two-sided alpha = 0.10 with no adjustment for multiple testing.

- 10.0 PHARMACOLOGY PLAN
- 10.1 Pharmacology Objectives
 - 10.1.1 Primary Objective
 - 10.1.1.1 To measure the PK of ruxolitinib in this population of **participants** with well-controlled HIV-1, and to characterize the relationship between ruxolitinib post-hoc estimated exposures (e.g., steady-state AUC = dose/CL/F) and immunological biomarkers of the study drug.
 - 10.1.2 Secondary Objectives
 - 10.1.2.1 To compare ruxolitinib PK parameters in study **participants** on specific ARV regimens to those reported for historical controls (no coadministered drugs) to assess the potential effect of ARV administration on ruxolitinib PK.
 - 10.1.2.2 To compare PK parameters of selected ARV medications (NNRTI's and INSTI's) when coadministered with ruxolitinib to historical controls (no coadministered drugs) in order to explore possible effects of ruxolitinib on ARV concentrations.

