### **4.2 Secondary Outcome Measures**

#### **4.2.1 Safety**

All summaries of secondary safety outcomes will be done in the safety analysis population.

In a similar manner to the primary safety analyses, tabular summaries will be provided for secondary outcomes (1-4), which will include frequencies and percentages overall and by study arm. Formal comparisons between study arms will contrast the proportion of participants who experienced any safety milestones on study from entry through week 12 as defined in secondary outcome (2) using a one-sided mid-p Fisher's exact test with 5% type-I error.

Levels and changes in safety laboratories (secondary outcomes 5 and 6) will be summarized with continuous descriptive summary statistics. Changes in safety labs will be formally compared at week 4/5 and week 10/12 via two-sided t-tests with 10% alpha and corresponding 90% confidence intervals.

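### Secondary safety outcome (4) is tabulated by arm but counts events of any grade that changed treatment, and the ruxolitinib route into that criterion exists only in Arm A

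*SAP*

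**What the plan says.** Secondary outcome (4) in SAP 2.4.2 covers protocol-defined reportable events at any time after entry: all diagnoses, Grade 3 or higher signs, symptoms or laboratory values, and "any signs/symptoms or laboratory values that led to a change in treatment or met ICH, EAE, or SAE guidelines". The last part comes from the reporting rules in the protocol. Protocol 6.3.5 makes reportable "any sign/symptom regardless of grade that led to a change in treatment", and Protocol 6.3.9 has a matching rule for laboratory values.

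SAP 4.2.1 says that "tabular summaries will be provided for secondary outcomes (1-4), which will include frequencies and percentages overall and by study arm". The only formal between-arm test of event proportions in that section is for "secondary outcome (2) using a one-sided mid-p Fisher's exact test with 5% type-I error". None is stated for outcome (4).

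Protocol 5.1 says "Study treatment is defined as ruxolitinib", and Arm B receives none. For the primary safety comparison, Protocol 9.6.1 keeps the composite "but with this composite safety outcome modified to address the A5336 design where Arm B does not receive any study treatment": stopping ruxolitinib for thrombocytopenia becomes Grade 2 or higher thrombocytopenia, and drug-related toxicity becomes toxicity of any cause. Primary and secondary outcomes (2) and (3) in the SAP carry these replacements.

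**The concern.** A definition built to trigger reporting is reused as a comparative outcome. As a reporting trigger it is sensible, because the team wants to hear of anything that alters dosing. As a by-arm percentage it sets a lower bar in one arm: an event below Grade 3 counts if someone changed the drug because of it, and Arm B has no study drug to change. The open-label design reinforces this, since participants and investigators know whether there is a drug to stop.

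SAP section 1 says that all primary and secondary outcomes will be submitted to ClinicalTrials.gov. A reader there may see one percentage per arm without this context and take the whole difference as a drug effect.

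**Working it through.** **1. Which routes exist in which arm**

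| Criterion in outcome (4) | Arm A | Arm B |
|---|---|---|
| Any diagnosis | yes | yes |
| Grade 3 or higher sign, symptom or laboratory value | yes | yes |
| Event meeting the SAE definition (Protocol 6.3) | yes | yes |
| Event leading to an ART change, if treatment includes ART | yes | yes |
| Event leading to a ruxolitinib change | yes | no |
| Expedited platelet criteria (Protocol 11.4.2) | yes | not settled |

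The criterion does not define treatment. On either reading, the ruxolitinib row is one-sided.

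**2. Whether events below Grade 3 can enter by that row**

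- Protocol 7.2.4 stops the drug for generalized bruising or unexplained bleeding, with no grade threshold.
- Protocol 7.1.1 provides for participants who choose to stop after a Grade 1 or 2 event.

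These two routes are enough to make the point. The creatinine clearance rule (7.2.3) is not relied on, because the grading table is not in the documents.

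Recording adds a little. After entry, Protocol 6.3.5 requires signs and symptoms only from Grade 2 upward, apart from non-traumatic bruising. A Grade 1 symptom that stops ruxolitinib is reportable in Arm A; the same symptom in Arm B need not be recorded.

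**3. Whether platelets add to it**

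The first dose reduction (7.2.1.2) and the stop (7.2.1.3) both require a fall of at least 25%. Protocol 11.4.2 lists falls of at least 25% from baseline for expedited reporting, and outcome (4) includes events that meet the expedited guidelines. If that list is applied in both arms, such falls qualify in both and the platelet route adds no asymmetry. The bullet names no arm, but the section names ruxolitinib as the agent, so the text does not settle it.

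**4. Illustration of size**

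The plan gives no figure for outcome (4). Its 80% power statement (Protocol 9.4.2) concerns the primary composite. Define:

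- r = risk of qualifying by criteria that apply in both arms;
- q = risk of some other, lower-grade event, equal in both arms and independent of the first;
- f = share of those events that lead to a ruxolitinib change in Arm A (zero in Arm B).

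Then Arm B = r, Arm A = r + (1 − r) × q × f, and the built-in gap = (1 − r) × q × f.

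With r = 10%, q = 20%, f = 50%:

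- gap = 0.90 × 0.20 × 0.50 = 9.0 points;
- Arm A = 19.0%, or 7.6 of 40;
- Arm B = 10.0%, or 2.0 of 20.

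Over r 5–20%, q 10–30% and f 25–100%:

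- smallest gap = 0.80 × 0.10 × 0.25 = 2.0 points;
- largest gap = 0.95 × 0.30 × 1.00 = 28.5 points, where every such event changes treatment.

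All three inputs are assumptions. If the ruxolitinib criterion is taken out of the by-arm count, the built-in gap is 0.

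**The case against.** The case for leaving the outcome alone has real weight:

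- **It is descriptive.** The change in Protocol 9.6.1 was made for a formally tested composite; outcome (4) has no test. That stands, so there is no type I error problem here.
- **Like-for-like comparisons already exist.** Outcome (2) is arm-neutral and tested, outcome (3) tabulates its components by arm, and changes in platelets, hemoglobin, neutrophils, liver enzymes and creatinine measures are compared at weeks 4/5 and 10/12. That stands and limits the harm, but it does not make the outcome (4) percentages comparable.
- **By-arm tabulation is blanket wording.** It also covers secondary outcome (1), which is limited to ruxolitinib by definition. True, but outcome (1) says so and outcome (4) does not.

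Some stronger readings are tempting and unsupported:

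- A reader might infer that an excess in Arm A is already known, or that Arm B must show zero. No results are given, and Arm B can qualify by the shared routes in the table.
- A reader might infer that dose changes for falling platelets drive the imbalance. Protocol 11.4.2 may bring the same falls into the count in Arm B, and an excess caused by a true fall on drug would be a signal, not an artefact.
- A reader might infer that the SAP dropped the protocol's by-grade comparison. The implementation plan in SAP Appendix 2 is redacted, SAP 1.1 lists no such change, and Protocol 9.6.2 still says "Comparisons of overall and toxicity-specific grades between study arms will be shown descriptively".

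**Conclusion.** The point holds in a limited form. Events that qualify for outcome (4) solely through a ruxolitinib change are counted in Arm A and cannot be counted in Arm B, so the by-arm percentages are not fully like for like. This follows from the text and needs no assumption about how treatment is defined. The protocol accepted the same reasoning for the primary composite.

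The size is unknown. The 9-point illustration and its 2.0 to 28.5 range rest on assumed rates and equal true risks; they show what the definition could produce, not what to expect. This is a cheap improvement to a descriptive outcome and leaves the tested safety comparisons untouched.

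**What to change.** - For the by-arm table and the posted result, count only criteria that apply equally in both arms: diagnoses, Grade 3 or higher events and SAEs. Include the platelet criteria in Protocol 11.4.2 only if they are applied in both arms, and say which.
- List events that qualify only through a ruxolitinib change separately, for Arm A alone.
- Keep the descriptive by-grade comparison of Protocol 9.6.2, for example as highest grade per participant, using the Grade 2 and higher data that Protocol 6.3.5 and 6.3.9 require without regard to arm.

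The cost is SAP wording and one listing from data already collected. The one drawback is that the tabulated definition would differ from the reportable-event label on the case report form, which a footnote can explain.

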7.0 CLINICAL MANAGEMENT ISSUES

7.1 Toxicity

Only toxicities related to the study **drug**, (ruxolitinib,) will be considered in the toxicity management section. The grading system is located in the Division of AIDS Table for Grading the Severity of Adult and Pediatric Adverse Events (DAIDS AE Grading Table), Version **2**.0, **November 2014**, located at the DAIDS R**S**C Web Site: http://rsc.tech-res.com/safetyandpharmacovigilance/

NOTE: The study core team must be notified by e-mail regarding toxicities that result in a change in regimen or discontinuation of study treatment ([contact]).

7.1.1 Grade 1 or 2

Participants who develop a Grade 1 or 2 AE or toxicity may continue study drug without alteration of the dosage, except as stated in sections 7.2.1 to 7.2.8. For **participants** experiencing Grade 1 or 2 AEs who choose to discontinue study drug, the site investigator should complete premature treatment discontinuation evaluations, and the **participant** should be encouraged to complete evaluations off treatment/on study.

NOTE: If **participants** discontinue study drug due to experiencing Grade 1 or 2 AEs, this should be noted in the CRF as the reason for discontinuation.

7.1.2 Grade 3

Participants who develop a Grade 3 AE thought to be related to the study drug should have their study medication **discontinued**. If the investigator has evidence that the AE has NOT been caused by study drug, study drug should be held until the AE or clinically significant laboratory abnormality is Grade ≤ 1 in severity, except as stated in sections 7.2.1 to 7.2.8 below.

If the same Grade 3 AE recurs at any time within 3 weeks after restarting treatment, the study drug must be permanently discontinued.

Participants experiencing Grade 3 AEs requiring permanent discontinuation of study drug should be followed weekly until resolution of the AE and should complete the premature treatment discontinuation evaluations and should be encouraged to complete off treatment/on study evaluations.

7.1.3 Grade 4

Participants who develop a Grade 4 symptomatic AE will have study drug permanently discontinued, except as stated in sections 7.2.1-7.2.8 below. **Participants** experiencing Grade 4 AEs requiring permanent discontinuation of study **drug** should be followed weekly until resolution of the AE and should complete the premature treatment discontinuation evaluations and the

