7.2.4 Bruising and Bleeding

For participants who report generalized bruising and/or symptoms of unexplained or abnormal bleeding, hematoma or epistaxis, the study drug should be discontinued.

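### SAP secondary outcome (4) counts low-grade events that changed treatment and is tabulated by arm, so a few kinds of event can count on ruxolitinib but not in Arm B

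*SAP*

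**What the plan says.** SAP 2.4.2 defines secondary outcome (4) as the occurrence, after entry, of adverse events that the protocol makes reportable. Besides all diagnoses and Grade 3 or higher signs, symptoms and laboratory values, it includes "any signs/symptoms or laboratory values that led to a change in treatment or met ICH, EAE, or SAE guidelines". SAP 4.2.1 then states that "tabular summaries will be provided for secondary outcomes (1-4), which will include frequencies and percentages overall and by study arm".

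The treatment-change criterion comes from the protocol's reporting rules. Protocol 6.3.5 makes reportable "any sign/symptom regardless of grade that led to a change in treatment". Protocol 6.3.9 has the matching rule for laboratory values, again with no grade floor.

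Protocol 5.1 says "Study treatment is defined as ruxolitinib", and Arm B receives none.

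For the composite safety outcome, the plan deals with this difference between arms. Under Protocol 9.6.1 the between-arm comparison uses a composite "modified to address the A5336 design where Arm B does not receive any study treatment": stopping ruxolitinib for thrombocytopenia becomes Grade 2 or higher thrombocytopenia, and the drug-relatedness condition on toxicities is removed. The SAP carries this through. Primary outcomes (1) and (2), and secondary outcomes (1) and (2), pair a ruxolitinib-only definition with a by-arm one. Secondary outcome (4) has a single definition for both uses.

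**The concern.** A criterion that depends on changing a drug cannot work the same way in an arm that does not take the drug. If the same low-grade event happens in both arms, it can count in Arm A because ruxolitinib was stopped, and go uncounted in Arm B because there was nothing to stop. Part of any difference between the two percentages would then come from the definition, and the overall percentage would mix two counting rules.

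Outcome (4) is the only general adverse-event outcome among the SAP's listed outcome measures, and SAP section 1 says that all primary and secondary outcomes will be submitted to the trial registry. What is at stake is how a reader interprets two descriptive percentages.

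**Working it through.** The documents state no rate, power or sample size for outcome (4), so there is no planned figure to reproduce. The check goes through the ruxolitinib actions in Protocol section 7 and asks whether the same event in Arm B would count by some other criterion.

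| Action on ruxolitinib | Trigger | Would the same event count in Arm B? |
|---|---|---|
| Platelet dose reduction (7.2.1.2) | Fall of at least 25% from baseline, count 150,000 to 200,000/mm³ | Yes: a fall of at least 25% is an expedited-reporting criterion (11.4.2) |
| Platelet stop (7.2.1.3) | Fall of at least 25%, count below 150,000/mm³ | Yes: both are expedited-reporting criteria |
| General holds and stops (7.1.2, 7.1.3) | Grade 3 or 4 | Yes, by grade |
| Anemia/neutropenia, diarrhea, lipids, glucose, AST/ALT (7.2.2, 7.2.5 to 7.2.8) | Grade 3 or higher | Yes, by grade |
| CNS abnormality, infection (7.3) | Mostly a diagnosis | Largely yes: diagnoses count in both arms |
| Confirmed virologic failure (7.5) | Not graded in the text | Not stated for outcome (4), but compared by arm in outcomes (2) and (3) |
| Bruising or bleeding (7.2.4) | No grade threshold | Not below Grade 3, unless another criterion applies |
| Voluntary stop (7.1.1) | Grade 1 or 2 | Not unless another criterion applies |
| Confirmed creatinine clearance below 60 mL/min (7.2.3) | No grade in the text | Depends on a grade that the documents do not give |

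The last three rows are what remains. Protocol 7.2.4 says that for participants who report "generalized bruising and/or symptoms of unexplained or abnormal bleeding, hematoma or epistaxis, the study drug should be discontinued". Protocol 7.1.1 provides for participants "experiencing Grade 1 or 2 AEs who choose to discontinue study drug". Bruising is the clearest case. After entry, only Grade 2 or higher signs and symptoms are recorded, "except record all non-traumatic bruising regardless of grade", so mild bruising is on record in both arms. If it is generalized, it should stop drug and so counts in Arm A; in Arm B the same record does not count.

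The direction follows from the definition. Let c be the probability that a participant meets a criterion available in both arms: diagnosis, Grade 3 or higher, ICH/EAE/SAE, or an ART change if that counts as treatment. Let r be the probability that a participant meets none of these but has a lower-grade event that changed ruxolitinib. With equal true event rates:

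- Arm A expected proportion = c + r
- Arm B expected proportion = c
- difference = r, which cannot be negative

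The documents give neither c nor r. The planned arm sizes show only what one participant is worth: 1/40 = 2.5 percentage points in Arm A and 1/20 = 5 points in Arm B. That is a scale, not an estimate of the gap. Without the treatment-change criterion, and with the remaining criteria applied alike, both arms have the same expected proportion and the artificial difference is 0.

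**The case against.** Outcome (4) carries no test, decision rule or sample size; under SAP 4.2.1 the formal week-12 comparison uses outcome (2). The composite was adapted because it is formally compared, so a descriptive row has less need of the same treatment. The outcome's own text names the treatment-change criterion, so an attentive reader knows what is counted. It says treatment rather than study treatment, so an ART change might qualify in Arm B.

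Comparisons that treat the arms alike also exist. Hemoglobin, platelets, neutrophils, AST, ALT, creatinine and creatinine clearance are recorded at every visit whatever the grade, and their changes are compared by t-test under outcomes (5) and (6). Protocol 9.6.2 plans descriptive comparisons of grades between arms. SAP section 5 lists further safety summaries, and the Analysis Implementation Plan that details them is redacted.

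Most of this stands and is why the point is small. It does not remove it. Counting ART changes leaves Arm A with an additional route, because both arms take ART and only Arm A also takes ruxolitinib. Other tables add context but do not alter what outcome (4) counts. A clear label tells the reader the rule, not how much of the difference the rule produced.

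**Conclusion.** The point holds in a limited form. Outcome (4) can count a small set of events below Grade 3 in Arm A and not in Arm B: chiefly generalized bruising or abnormal bleeding and voluntary stops after Grade 1 or 2 events, and possibly holds for low creatinine clearance. The bias is toward more apparent harm on ruxolitinib, in a descriptive comparison only. This is a worthwhile, cheap improvement rather than a flaw in a primary result.

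A reader might infer more, in three ways that the documents do not support.

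- That dose reductions and temporary holds widen the gap. The platelet reduction largely qualifies anyway through expedited reporting, and most mandated holds begin at Grade 3, where both arms follow the same rule.
- That the EAE criterion is itself uneven, because Protocol 11.4.2 names only ruxolitinib as the agent. The reporting scope is set by the DAIDS EAE Manual, which is not among the documents. Silence about Arm B does not show unequal reporting.
- That the gap can be sized from the 20% allowance in Protocol 9.4.1. That figure combines loss to follow-up with treatment discontinuation and serves the IL-6 evaluable sample. It is not an adverse-event rate, and no share of it is attributed to low-grade events.

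The conclusion assumes that the expedited-reporting criteria are applied alike in both arms and that ART changes are about equally frequent. It also assumes that the reporting rules of protocol version 2.0 still apply. The SAP reflects later changes in places, such as a 45-day rather than 30-day CD4 window.

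**What to change.** Split secondary outcome (4) as the SAP already splits outcomes (1) and (2):

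- **(4a) Ruxolitinib arm only:** reportable adverse events as now defined, including those that changed treatment.
- **(4b) By arm:** all diagnoses, Grade 3 or higher signs, symptoms and laboratory values, and events meeting ICH, EAE or SAE criteria, without the treatment-change criterion.

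Amend SAP 4.2.1 so that the by-arm tabulation refers to (4b). It would also help to cite there the table that delivers the by-arm grade comparison of Protocol 9.6.2, wherever it sits, since that is where recorded low-grade events, bruising included, can be compared on equal terms.

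The cost is one extra descriptive row from data already collected, with no change to any test. The downside is that low-grade events that led to stopping drug leave the by-arm row. They remain in (4a), and discontinuations also remain in the participant listing with reasons under SAP 4.1.2.
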